7.7.2 Post-Intervention

For surgical cohort participants, liver resection surgery and post-surgical observation should follow institutional standards of care and good clinical practice. After liver resection, a portion of the liver specimen that does not contain tumor and consists of at least 1 gram of liver tissue will be placed in RNAlater (Qiagen). One other section of non-tumor bearing liver tissue measuring at least 1 cm x 1 cm x 0.5 cm will be placed in formalin and stored in the refrigerator.

Non-surgical cohort participants will undergo a post-intervention percutaneous or transjugular biopsy of their cirrhotic/fibrotic liver in a non-tumor bearing area. Participants should remain NPO after midnight before the scheduled biopsy to allow for use of conscious sedation if indicated. Whether to perform the biopsy under local anesthesia or under conscious sedation will be at the discretion of the clinician performing the biopsy. For percutaneous biopsies, a 16-gauge core is preferable; an 18-gauge core is acceptable. All participants will be monitored post-procedure according to institutional standards of good clinical practice, after which time they may be discharged to home. Percutaneous biopsy may be conducted under ultrasound guidance. Whether by percutaneous or transjugular approach, biopsies will consist of a minimum of 2 samples. Four (4) samples is preferable. The first two samples will be placed in formalin. The second two will be placed in RNAlater (Qiagen). The four samples will be stored in a refrigerator. If the clinician performing a percutaneous biopsy is unable to obtain the first two core biopsies safely (e.g. participant starts bleeding), the clinician should abort the attempt. The participant will be considered not evaluable.

8. CRITERIA FOR EVALUATION AND ENDPOINT DEFINITION

8.1 Primary Endpoint

To find the safe and minimum effective dose (MED) that achieves at least a 40% response rate, where a response is defined as an evaluable participant that achieves at least a 50% reduction in liver phospho-EGFR staining, defined as the percentage of positive pixels, from baseline after a 7-day intervention period with daily erlotinib. See Section 13.6 for definition of evaluability for this endpoint.

8.2 Secondary Endpoint

- To assess the overall adverse event profile for erlotinib.

8.3 Translational/Exploratory Endpoints:

- To assess the relationship between dose-level and staining of phospho-ERK, PCNA, EGF, and α SMA in the liver
- To assess relationship between dose and modulation of a gene expression signature associated with prognosis in cirrhosis.
- To determine whether erlotinib is associated with a measurable reduction in viral load in participants with HCV+.
- To determine the relationship between erlotinib dose-schedule and erlotinib plasma level on the day of liver resection.

8.4 Off-Agent Criteria

Participants may stop taking the study agent due to: completion of the planned intervention period, development of an adverse event or serious adverse event, inadequate agent supply, noncompliance, use of concomitant medications, medical contraindication, refusal, ineligibility (see Section 8.5), major treatment violation (see Section 8.5) or alternative treatment. Participants will continue to be followed, if possible, for safety according to the intended schedule of events (see Section 7).

Participants discontinuing the planned intervention prematurely will be encouraged to complete the Post-Intervention Evaluation tests and procedures as appropriate (if participant does not refuse, is not lost to follow-up, or unless it is clinically contraindicated). See Section 8.5 for further details as to data submission for participants deemed Ineligible after starting treatment or classified as a Major Treatment Violation (i.e., protocol requirements regarding intervention during the first week post-randomization were severely violated).

8.5 Off-Study Criteria

Participants may go "Off-Study" for the following reasons: development of an adverse event or serious adverse event, death, lost to follow-up, participant withdrawal, physician decision, protocol violation, complete study, or other (with detailed comments provided). Reason(s) will be noted in the participant's research records, with the primary reason clearly identified. The participant will be classified as (Off Study/Off Agent). Data submission and follow-up after participants are determined to be "Off-Study/Off-Agent" for specific situations is noted below:

A registered participant is deemed ineligible if the participant did not satisfy each and every eligibility criterion at the time of study entry, for example, identified based on an audit or through the case evaluation process.

- If participants received study intervention, on-study materials and all data up until the point of confirmation of ineligibility will be submitted.
- If participants did not receive study intervention, on-study materials must be submitted. No further data submission is necessary. No follow-up is required.

Major Treatment Violation: A registered participant is deemed as being in major treatment violation by the coordinating center, if the participant's very first treatment/intervention administration is so grossly administered in error, that the participant's data can no longer be used for the primary endpoint. These cases are typically rare.

- On-study material and all data up until the point of confirmation of a major violation must be submitted.

Cancel/Participant Withdrawal: A registered participant is deemed a cancel if he/she refuses the study or withdraws consent before any study intervention is given. On-study material must be submitted. The Off Study case report form must be submitted. No follow-up is required.

8.6 Study Termination

NCI, DCP as the study sponsor has the right to discontinue the study at any time. The FDA also has the ability to discontinue the study at any time.

9. CORRELATIVE/SPECIAL STUDIES

9.1 Rationale for Methodology Selection

Gene signature assay: A total of 200ng RNA will be analyzed for the 186-gene liver signature by using nCounter Digital Analyzer system (NanoString) at the UT Southwestern/Simmons Cancer Center shared core facility. A scanned profile with median transcript count <100 will be regarded as having poor quality, and excluded from subsequent analysis. Scanned data will be normalized by scaling the transcript counts with geometric mean of built-in normalization genes by using NanoString normalizer module implemented in GenePattern genomic analysis toolkit (15). Suppression of the 186-gene signature will be quantitatively evaluated for each patient by comparing the paired specimens obtained before and 7 (5-14) days after starting the erlotinib treatment using nearest template prediction algorithm (14) implemented in GenePattern genomic analysis toolkit. A prediction of good prognosis with prediction confidence p-value <0.05 for the day 7 specimen will be regarded as statistically significant suppression of the gene signature in response to the erlotinib treatment.

Assessment of phospho-EGFR staining: Whole slide high-resolution imaging will be performed on the pre-and post-treatment biopsy slides/samples (Aperio, Leica Microsystems Inc. Buffalo Grove, IL 60089 United States). The Positive Pixel Count algorithm will be used quantify the amount of the positive staining on the pEGFR preparation (<http://cancerpreventionnetwork.org/sc.shtml>) three intensity ranges (220-175, 175-100, and 100-0). Only pixels with the strongest intensity (100-0) will be chosen for analysis. Pixels which are stained, but do not fall into the positive-color specification will be considered as negative stained pixels—these pixels will be counted and the fraction of positive pixels to total pixels will be determined. A pseudo-color markup image generated by the algorithm will be examined allowing for confirmation that the desired color and intensity ranges are recorded. Only hepatocytes will

be evaluated and portal tracts will be excluded from analysis. A meaningful reduction in the phospho-EGFR staining is defined as a 50% reduction in positive pixel to total pixel ratio relative to pre-erlotinib baseline.

If multiple specimens from a single participant are analyzed, the specimens showing the most significant reduction in percentage of positive pixels in response to erlotinib will be used for analysis. The rationale is that this pilot study is looking for evidence of a signal (i.e. a reduction in phospho-EGFR staining that indicates an effect on the pathway).

- Cell lines and/or tissue that are positive and negative for phospho-EGFR will serve as a positive and negative control.
- Allowable formalin fixation time for needle biopsy specimens: 4 to 24 hours
- Allowable formalin fixation time for resected liver specimens: 24 to 48 hours.
- All sections for staining should be cut at 10 microns.

In the nonsurgical cohort, positive **phospho**-EGFR assessment for initial eligibility will be defined as a minimum of 100 stained pixels.

For the immunohistochemical staining of paraffin-embedded liver tissues, the following antibodies will be used: phospho-EGFR:

- Cell Signaling - #2236 (mouse monoclonal). This detects phosphorylation at Tyr1068.
- phospho-ERK: Cell Signaling - #9101 (rabbit polyclonal) - which detects phosphorylation at Thr202/Tyr204
- PCNA: Cell Signaling - #2586 (mouse monoclonal)
- EGF: R&D Systems - #MAB236 (mouse monoclonal)
- α SMA: DakoCytomation #M0851 (mouse monoclonal). An alternative that has also been successful is Abcam #ab5694 (a rabbit polyclonal), which will be employed if necessary.

Note: Heavier or darker staining is commonly seen along the edges of IHC stained tissue sections. This is an artifact in the staining. Under the guidance of an Anatomic Pathologist, this artifact is avoided in selecting the analysis region for each slide.

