2.3 Rationale

Preliminary Data:

- Gene-expression profiles in patients with cirrhosis and resected HCC demonstrate that the surrounding non-tumoral liver tissues contain a gene expression signature that identifies those patients most likely to die from complications of cirrhosis (10). The 186-gene cirrhosis prognosis signature consists of a 73-gene poor-prognosis signature and 113-gene good-prognosis signature. This signature was developed in a training set of 82 Japanese patients and validated in a set of 225 patients from the U.S. and Europe. The EGF gene is a significant component of this signature, and those with high EGF expression in their liver tissue have worse survival (10).
- The EGF gene SNP 61*G (rs4444903) is a functional SNP. In cirrhosis patients, the number of G alleles correlates with serum and liver EGF levels; subjects with G/G genotype have higher EGF levels than those with G/A genotype, who have higher levels than those with A/A genotype. This SNP correlates with risk for HCC in cirrhosis patients: those with G/G genotype have a greater risk for

HCC than those with G/A genotype, who have a higher risk than those with A/A genotype. This correlation was confirmed in a set of patients from the U.S. and an independent set of European patients (11). We have collaborated with a group at Nagoya University and recently demonstrated that HCC risk correlates with the EGF SNP in a Japanese cirrhotic patient population.

- Subjects from the Hepatitis C Antiviral Long-term Treatment against Cirrhosis (HALT-C) trial (n = 816) that were followed prospectively for development of HCC were analyzed for EGF SNP. Using a Cox proportional hazards model, the EGF SNP was found to correlate with risk for HCC. A prediction model was developed that includes the EGF genotype to identify patients at low, intermediate, and high risk for HCC; 6-year cumulative HCC incidences were 2.3%, 10.4%, and 26%, respectively (11).

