10.2.2 Research Tissue Specimens

10.2.2.1 Surgical Cohort – Pre-Intervention

The pre-intervention percutaneous or transjugular liver biopsy may be conducted under ultrasound guidance following institutional standards of care before, during, and after the procedures. The collected specimens will consist of 4 specimens, of which 2 will be placed in RNAlater (Qiagen), and the other two will be placed in formalin. All four samples will be clearly labeled with study number, participant ID, specimen type, and date and time of collection. The RNAlater samples will be stored in a refrigerator at the participating site until shipped to the BAP Lab. The BAP Lab will store samples in a -80°C freezer until sent to [name] lab.

The formalin samples will be embedded in paraffin within 24 hours. The date and time of collection as well as paraffin embedding will be recorded on the Specimen Submission: Tissue case report form. Paraffin blocks will be shipped on a cool pack to the Mayo Clinic (CPN PC Office, address below) for accessioning. The PC office will forward blocks and cores to the Mayo Clinic PRC in one batch at the end of enrollment for each cohort.

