10.2.2.3 Non-Surgical Cohort – Pre-Intervention

After informed consent and pre-registration, specimens from the clinical biopsy (paraffin block or ten (10) 5-micron unstained slides and 1 H&E) will be obtained and submitted to the CPN Pathology Coordinator for assessment. The pathology coordinator will ship immediately to Mayo Clinic PRC (Attention: [name]) for real-time (≤ 21 days from collection) phospho-EGFR assessment to determine eligibility. At this time, one or two slides will be cut from the block for the purposes of determining eligibility. The rest of the block will remain intact and be cut at the time of dose-level efficacy analyses (post-intervention). Results will be returned to CPN PC for entry into the database. If the assessment of the pre-intervention specimen is positive (See Section 7.3 for definition), the participant will be allowed to continue the screening process.

All samples will be clearly labeled with study number, participant ID, specimen type, and date and time of collection.

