10.2.2.4 Non-Surgical Cohort – Post-Intervention

The post-intervention percutaneous or transjugular liver biopsy may be conducted following institutional standards of care before, during, and after the procedures. The collected specimens will consist of 4 samples. Two will be placed in RNAlater (Qiagen), and the other two will be placed in formalin. All specimens will be clearly labeled with study number, participant ID, specimen type, and date and time of collection. The RNAlater samples will be stored in a refrigerator at the participating sites until shipped to the BAP Lab. The BAP Lab will store samples in a -80°C freezer until sent to [name] lab (upon request).

The fresh formalin samples will be embedded in paraffin within 24 hours. The date and time of collection as well as paraffin embedding will be recorded on the Specimen Submission: Tissue case report form. Paraffin blocks will be shipped refrigerated to the Mayo Clinic (CPN PC Office, address below) for accessioning.

At the same time, the paraffin block containing the specimen used to establish initial eligibility at baseline will be submitted to the CPN PC Office. Additional sections are required because it is critical

that specimens used for efficacy analysis at the end of each dose level be cut for both time points and for all participants at the same time.

Institutions unable to submit paraffin blocks may submit one 3.0mm to 4.0mm core taken from each block and placed into individual 2mL tubes. If cores cannot be provided, cut one H&E and 10 sections at 5 microns and mount on charged slides.

Notes:

- For institutions that must, per institutional policies, provide cores or slides instead of paraffin blocks: **Do not create the cores or cut slides until requested to do so by the CPN Pathology Coordinator.** Analysis for the study endpoints requires all slides for both time points for all participants to be sectioned at the same time.
- **Note: Sites are to notify CPN Pathology Coordinator ([name]; [contact]; [contact]) when specimens are shipped for tracking purposes.**

Post-intervention paraffin blocks (or cores) will be shipped from the CPN PC Office to the PRC at the Mayo Clinic in the same batch as the pre-intervention specimens at the conclusion of enrollment for each dose level.

Shipping Destination Summary:

Pre- and post-intervention paraffin blocks (or cores or unstained and H&E slides) will be shipped from all participating sites to:

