13.5 Secondary and Translational/Exploratory Endpoints

The secondary endpoint is to assess the complete adverse event profile for erlotinib.

Translational endpoints consist of the following:

- To assess the relationship between dose-level and staining of phospho-ERK, PCNA, EGF, and α SMA in the liver
- To assess relationship between dose and modulation of a gene expression signature associated with prognosis in cirrhosis.
- To determine whether erlotinib is associated with a measurable reduction in viral load in participants with HCV+.
- To determine the relationship between erlotinib dose-schedule and erlotinib plasma level on the day of liver resection.

Analysis Methods: The translational endpoints will be assessed from tissue samples. Data for these translational endpoints will be considered hypothesis generating and/or exploratory in nature. We will compare the baseline biomarker expression levels (e.g. staining of phospho-ERK, PCNA and α SMA; gene expression signature; viral load) across all the dose levels using analysis of variance (ANOVA) or the nonparametric equivalent. We will also assess the changes in these biomarker values from baseline to Day 7 using the Wilcoxon Signed-Rank test and compare these changes across dose levels using ANOVA (or the nonparametric equivalent). Graphical methods will also be used to assess the differences in these biomarker values across dose levels. All categorical variables will be analyzed using chi-square or Fisher's exact tests.

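### The Section 9.1 rule for gene-signature suppression looks only at the day 7 specimen, so a participant already good-prognosis before erlotinib and unchanged counts as suppressed by it (exploratory endpoint)

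*Combined protocol and SAP*

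**What the plan says.** Section 9.1 describes the gene-signature assay in two steps. It first says that suppression will be evaluated for each patient by "comparing the paired specimens obtained before and 7 (5-14) days after starting the erlotinib treatment", using nearest template prediction. It then gives the only significance criterion: a good-prognosis prediction with "prediction confidence p-value <0.05 for the day 7 specimen will be regarded as statistically significant suppression of the gene signature", attributed to erlotinib.

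Section 2.3 describes the signature as one that "consists of a 73-gene poor-prognosis signature and 113-gene good-prognosis signature". It was developed and validated in patients with cirrhosis and resected HCC, and that description makes no reference to erlotinib.

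Section 13.5 includes the signature among the translational biomarkers. It plans to "assess the changes in these biomarker values from baseline to Day 7 using the Wilcoxon Signed-Rank test" and to compare those changes across dose levels. It adds that these data "will be considered hypothesis generating and/or exploratory in nature".

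On specimens, Section 10.2.2.1 provides four pre-intervention cores in the surgical cohort, "of which 2 will be placed in RNAlater (Qiagen), and the other two will be placed in formalin". For the non-surgical cohort, Section 10.2.2.3 takes the baseline from existing material: "specimens from the clinical biopsy (paraffin block or ten (10) 5-micron unstained slides and 1 H&E) will be obtained". After treatment that cohort does have fresh cores (Section 10.2.2.4): "Two will be placed in RNAlater (Qiagen), and the other two will be placed in formalin".

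**The concern.** The first step promises a paired comparison, but the criterion that follows does not use the pair. A confident good-prognosis call at day 7 satisfies it whatever the baseline call was. The good-prognosis pattern occurs in patients irrespective of erlotinib, so such a call can precede treatment. The trial has a single arm and no randomization (Section 13.2), so each participant's own baseline is the only available reference, and the label leaves it out.

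The label is described as statistically significant and attributed to the drug. Section 13.4 says that the translational results will help plan a larger study. A per-patient suppression rate that includes people in whom nothing changed would mislead that planning. Dose selection is not affected, because the MED rests on phospho-EGFR response and DLTs.

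**Working it through.** **1. Does any other provision supply the missing baseline condition?**

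- *Eligibility (Sections 4.1 to 4.4).* There is no gene-signature criterion. Entry is by fibrosis or cirrhosis up to Child-Pugh A, together with organ function and, in the non-surgical cohort, positive phospho-EGFR staining. Participants already good-prognosis can enter.
- *The paired-comparison sentence in 9.1.* It names the specimens to compare but gives no rule for the result. The rule comes in the next sentence and uses only the later specimen.
- *Section 13.5.* It tests change in biomarker values and does not redefine the label. For categorical variables it names chi-square or Fisher's exact tests, and no paired method.
- *Contrast with phospho-EGFR.* Section 9.1 defines that response as a 50% reduction relative to baseline. Section 13.6 requires baseline staining in the surgical cohort so that a reduction is possible. The signature label has neither safeguard.

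**2. Size of the effect.** The plan states no rate, power or sample size for this label, so there is no figure to reproduce. Let q be the share confidently good-prognosis at baseline. The documents do not give q; 10% to 50% is assumed. With no drug effect and stable calls, the expected share labelled suppressed is q.

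| Assumed q | Of 10 at a dose level (10q) | Of 31, the adjusted target accrual in Section 13.3 (31q) | P(at least 1 of 5) = 1 − (1 − q)^5 | P(at least 1 of 10) = 1 − (1 − q)^10 |
|---|---|---|---|---|
| 10% | 1 | 3.1 | 0.41 | 0.65 |
| 30% | 3 | 9.3 | 0.83 | 0.97 |
| 50% | 5 | 15.5 | 0.97 | 0.999 |

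If the label also required a baseline call that was not confidently good, each entry would be 0 under the same assumptions.

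**3. Unstable calls.** Suppose a fraction f of calls that are not good at baseline become confidently good through sampling or assay noise alone, while good calls stay good. The present rule then reports q + (1 − q)f. The amended rule, with its restricted denominator, reports f. At an assumed q = 30% and f = 10%, that is 0.30 + 0.70 × 0.10 = 37% against 10%. The baseline condition removes the q part but not the noise.

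**4. Is there baseline RNA to condition on?** The Specimen Collection Summary Chart lists pre-intervention RNAlater cores for the surgical cohort only. RNA isolation is described for RNAlater specimens (end of Section 10.2.2.4). As written, a non-surgical participant could be labelled suppressed from a post-treatment core with no baseline RNA.

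**The case against.** The strongest reply is that the criterion should be read within its paragraph. The preceding sentence already calls for a paired evaluation, and suppression in response to treatment presupposes a change. On that reading p<0.05 is only the confidence threshold inside a paired comparison, and the fault is one of drafting. The inferential analysis in Section 13.5 is referenced to baseline, the endpoint is the relation of dose to modulation of the signature, and no section says that a suppression rate will be reported. The size given above simply returns the assumed q. The zero after the fix depends on stable calls, which is doubtful when the surgical cohort compares a needle core with resected tissue. RNA from the non-surgical paraffin block is not excluded: Section 10.2.2.3 keeps the rest of the block intact, and the title of the signature's source refers to fixed tissues.

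Much of this limits the consequence, and it stands. The data are exploratory, the group-level analysis of change is sound in principle, q is unknown, and the baseline RNA gap in the non-surgical cohort is possible rather than established. None of it supplies a baseline condition. A statistician who applies the criterion as written will label unchanged participants as suppressed. The noise objection also applies to the present rule, which carries the q part in addition.

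**Conclusion.** The concern holds. The per-patient label in Section 9.1 is a stated rule that gives a wrong answer for anyone confidently good-prognosis both before and after treatment. With no drug effect and stable calls, the rate it produces equals q: 10%, 30% or 50% at the assumed values, or about 3, 9 or 16 of 31 if all 31 have a usable day 7 profile. Fewer would be affected if some profiles are missing or fail the quality threshold.

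The finding is confined to this label. It does not extend to the analysis of change in Section 13.5, to the phospho-EGFR endpoint, or to any MED or safety decision. The label should be corrected because it would be reported as a significant effect of the drug.

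**What to change.** In Section 9.1, define suppression as a shift from not meeting good prognosis with p<0.05 at baseline to meeting it at day 7. Leave out of the denominator participants already good-prognosis with p<0.05 at baseline and those without usable baseline RNA. Tabulate baseline calls against day 7 calls by dose level, so that shifts in the opposite direction are visible and give some indication of noise. Because the amended label still rests on single-specimen p-values, refer to the paired change analysis in Section 13.5 for inference about dose.

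This costs a rewritten criterion, a cross-reference and one table, with no new specimens. The drawback is a lower rate on fewer participants. If only surgical participants have baseline RNA and they make up a share s of the 31, the denominator is 31 × s × (1 − q). Both s and q are assumed:

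| s | q = 10% | q = 30% | q = 50% |
|---|---|---|---|
| 25% | 7.0 | 5.4 | 3.9 |
| 50% | 14.0 | 10.9 | 7.8 |
| 75% | 20.9 | 16.3 | 11.6 |

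Section 9.1 should also state whether RNA from the non-surgical baseline blocks will be used. If it can be, fewer participants are lost.
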